5.1.6 Patient Health Questionnaire depression scale (PHQ-8)

The 8 item PHQ-8 Assessment (see Appendix 1) will be completed by the subject at the following visits:

Screening, Baseline, Week 4, and Week 8

A subject with a PHQ-8 score of '15' or above should be referred promptly to a mental health care professional and, if currently applying investigational product, consideration should be given to discontinuation from investigational product.

Subjects with PHQ-8 \geq 10 at Screening or Baseline will be excluded from the study.

PHQ-8 score is the sum of the responses for the 8 questions.

Five severity categories of depression are defined as follows:

- None Minimal depression (0 to 4)
- Mild depression (5 to 9)
- Moderate depression (10 to 14)
- Moderately severe depression (15 to 19)
- Severe depression (20 to 24)

5.1.7 Columbia-Suicide Severity Rating Scale (C-SSRS)

C-SSRS Assessments will be performed as follows:

Screening, Baseline, Week 4, and Week 8.

The administration schedule of the C-SSRS will be:

- The Baseline-Screening version (Appendix 2) will be used at Screening to provide a pretreatment assessment baseline.
 - If a subject has a score greater than 0 in suicidal ideation, this is important and may indicate the need for mental health intervention. The Investigator should give consideration to not enrolling the subject in the study.
- On all subsequent visits, the Since Last Visit version (Appendix 3) will be used.
 - Any score greater than 0 in the suicidal ideation score is important and may indicate the need for mental health intervention and consideration be given to discontinuation from IP. This should result in prompt referral to a mental health professional and/or possibly the emergency room. The Medical Monitor should be contacted.

The trained administrator will conduct the C-SSRS. The C-SSRS administrator will be trained via the C-SSRS training video. A training certificate for the administer(s) will be on file in the trial master file at the site.

An Investigator must review the completed C-SSRS. A qualified mental health care provider must be available, immediately if needed, to refer the subject for further evaluation.

5.1.8 Local Tolerability Assessments

The Investigator Local Tolerability Assessment will be an overall assessment of local tolerability and performed as follows:

Baseline, Weeks 4 and 8

Application site reactions will be graded at the timepoints outlined in the Schedule of Visits and Assessments (Section 1.3). Irritation reactions are graded using the scale detailed in the following section (Berger 1982). Reactions at the site of product application, which may occur post-Baseline, should be differentiated from the preexisting inflammation associated with the subject's seborrheic dermatitis.

The Investigator assessments will be conducted by the Investigator prior to any investigational product application in the study site.

Dermal Response

- 0 = no evidence of irritation
- 1 = minimal erythema, barely perceptible
- 2 = definite erythema, readily visible; minimal edema or minimal papular response
- 3 = erythema and papules
- 4 = definite edema
- 5 = erythema, edema and papules
- 6 = vesicular eruption
- 7 = strong reaction spreading beyond application site

Other Effects

- A = slight glazed appearance
- B = marked glazing
- C = glazing with peeling and cracking
- D =glazing with fissures
- E = film of dried serous exudates
- F = small petechial erosions and/or scabs
- G = no other effects

The Subject Local Tolerability Assessment will be an overall assessment of local tolerability and performed as follows:

Baseline, Weeks 4 and 8

This assessment will be administered at Baseline by the site 10 to 15 minutes after IP application at the study site. Assessments at the study site during Weeks 4 and 8 will be a recall assessment of the subject's experience 10-15 minutes after IP application since the last study visit.

Grade	Sensation Following Investigational Product Application
0 (none)	No sensation
1 (mild)	Slight warm, tingling sensation; not really bothersome
2 (moderate)	Definite warm, tingling sensation that is somewhat
	bothersome
3 (severe)	Hot, tingling/stinging sensation that has caused definite
	discomfort

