1.3 Schedule of Visits and Assessments

Study Procedure	Screen	Baseline Day 0	Wk 2 Day 14	Wk 4 Day 28	Wk 8 Day 56	Wk 9 Day 63
Visit	1	2	3	4	5	6
Visit Window	-4 weeks		+/- 3 day	+/- 5 days	+/- 5 days	+/-5 days
Informed consent/assent	Х					
Medical history	Х					
Physical examination ^a	Х	Х			Х	
I/E criteria	Х	Х				
Randomization		Х				
Hematology, Serum Chemistries, and Urine Analysis	Х	Х			Х	
Vital signs, height, weight ^b	Х	Х	X	Х	Х	Х
IGA ^c , Overall Assessment of Erythema ^c , Overall Assessment of Scaling ^c	Х	Х	Х	Х	Х	Х
WI-NRS, DLQI, Scalpdex	Х	Х	Х	Х	Х	
BSA	Х	Х			Х	
Application Site Reaction Assessment/Local Tolerability ^d		Х		Х	Х	
Pigmentation Assessment ^e	Х	Х	Х	Х	Х	Х
C-SSRS, PHQ-8	Х	Х		Х	Х	
Medical Photography ^f		Х	Х	Х	Х	
Pregnancy test ^g	Х	Х		Х	Х	
PK draws ^h		Х		Х	Х	
IP/vehicle application at the study site ⁱ		Х	Х			
Dispense study medication kit ^j		Х	X	Х		
Dispense/review diary		Х	X	Х	Х	
Weigh study medication kit ^k		Х	X	Х	Х	
Compliance calculation ¹		Х	Х	Х	Х	
Adverse event assessment	Х	Х	Х	Х	Х	Х
Concomitant medications	Х	Х	Х	Х	Х	Х

Footnotes:

^a Limited physical examination: skin, lungs, and heart only

- ^b Height will be collected at Baseline and Week 8. Weight will be collected at all study visits. Subject to void prior to weight being taken. Remove any jackets, outerwear and shoes. Remove any objects of significant weight (i.e. cell phones, wallet, key chains). A 5% weight loss from Baseline should be reported to the medical monitor.
- ^c IGA will be a 5-point scale ranging from clear (0) to severe (4). IGA should be completed prior to other physician assessments. Overall assessment of erythema (0-3 scale) and overall assessment of scaling (0-3 scale) will be completed.
- ^d Local tolerability Assessments: The Investigator local tolerability assessment of skin irritation (Berger and Bowman skin irritation score) should be performed prior to the investigational product application at Baseline, and at Weeks 4 and 8. Reactions at the site of product application, which may occur post-Baseline, should be differentiated from the preexisting inflammation associated with the subject's seborrheic dermatitis. Subjects will perform the local tolerability assessment 10-15 minutes post-drug application at Baseline, and recall assessments at Weeks 4 and 8 for the subject's '0-3' burning/stinging assessment.

Protocol ARQ-154-203 Amendment 1

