4.3 Subject Participation

There will be a minimum of 6 clinic visits, including Screening, Baseline, Week 2, Week 4, and Week 8 of treatment, as well as a Week 9 follow-up visit (1 week after last dose). Since the

interval between the Screening and Baseline visits may be up to 4 weeks, the anticipated maximum duration of subject participation is \sim 13 weeks.

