4.6.3 Treatment Administration

At the randomization visit (Baseline visit), the study staff will demonstrate to the subject how to apply ARQ-154 foam or vehicle foam using the first container from the kit that is assigned to the subject at randomization. Study site staff will be trained to ensure a proper amount is dispensed from the foam can and applied to seborrheic dermatitis lesion(s) as a thin film and rubbed in thoroughly but gently, until the 'white' has disappeared. For scalp lesions, special attention should be given to ensuring adequate investigational product is applied to scalp skin and not rubbed off on hair. The subject will then practice dispensing a similar amount of investigational product and applying to seborrheic dermatitis lesion(s). The study staff will confirm that the subject's application technique is correct.

IP will be applied QD in the evening (except at Baseline and Week 2, in which case IP will be applied at the study site) to areas of lesions of seborrheic dermatitis. IP will be applied at least 20 minutes before going to bed.

For Scalp Lesions: IP will be applied when the skin and hair on the scalp is dry. Subjects should dispense IP on their fingers, then part hair where there are lesions and rub in. Subjects should not use other hair products for at least an hour before or after application. Subjects should maintain treatment of areas with the IP for the duration of the study regardless of whether treatable areas of seborrheic dermatitis clear.

For Non-scalp Lesions: IP should be applied QD to affected areas and rubbed in until disappeared. Subjects should maintain treatment of areas with IP for the duration of the study regardless of whether treatable areas of seborrheic dermatitis clear.

Re-training will be conducted at subsequent visits as needed (i.e., if the returned pump(s) weighs substantially different than the expected weight).

Subjects should not wash areas (or otherwise expose to water, eg, swimming) where ARQ-154 foam or vehicle has been applied until at least 4 hours after IP application and preferably not until the following morning.

Subjects should continue to apply the IP to all treatment areas identified by the Investigator at Baseline using a Body Diagram even if that area has cleared during the treatment period. New plaques that develop during the study should be treated as well.

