5.7 Adverse Events

5.7.1 Adverse Event Definition

An AE means any untoward medical occurrence associated with the use of a drug in humans, whether or not considered drug related. An AE can therefore be any unfavorable and unintended sign (including an abnormal laboratory finding), symptom, or disease temporally associated with the use of a medicinal (investigational) product, whether or not related to the medicinal (investigational) product.

AEs will be collected following informed consent of the subject through subject study completion.

A treatment emergent adverse event (TEAE) is defined as an AE that started post application of IP at the Baseline visit through study completion.

Application site reactions will be considered adverse events if they require intervention, suspension or discontinuation of IP.

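### The Week 4 tolerability recall reaches back only to the Week 2 visit, so the subject's 0-3 burning/stinging scale does not cover home applications on about Days 1-13

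*Protocol*

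**What the plan says.** Protocol section 5.1.8 sets the subject's local tolerability rating at Baseline, Week 4 and Week 8.

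- **Baseline:** "This assessment will be administered at Baseline by the site 10 to 15 minutes" after the application made at the site, so this rating concerns the first application only.
- **Weeks 4 and 8:** the assessment "will be a recall assessment of the subject's experience 10-15 minutes after IP application since the last study visit".

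In section 1.3, the row "Application Site Reaction Assessment/Local Tolerability" is marked at Baseline, Week 4 and Week 8; the Week 2 cell is empty. Footnote d provides for "recall assessments at Weeks 4 and 8 for the subject's '0-3' burning/stinging assessment" and gives no look-back period.

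Week 2 is nonetheless a study visit. Section 4.3 states: "There will be a minimum of 6 clinic visits, including Screening, Baseline, Week 2, Week 4, and Week 8 of treatment". Section 4.6.3 places routine dosing at home in the evening, "except at Baseline and Week 2, in which case IP will be applied at the study site".

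Section 5.7.1 sets the rule for adverse event reporting: "Application site reactions will be considered adverse events if they require intervention, suspension or discontinuation of IP". Section 6.4.2 summarizes the tolerability scores descriptively by visit.

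**The concern.** The recall period is tied to the previous visit, while the ratings are not made at every visit. The visit before Week 4 is Week 2, where nothing is rated. The Week 4 question therefore does not reach back to the previous rating, and a stretch between the two is left open.

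That stretch is the first two weeks of home use. This is the first study of the foam, which is applied to the face, scalp, trunk and intertriginous skin, and local tolerability is one of the listed safety measures. A reader of a by-visit table would naturally take the Week 4 column to describe treatment so far. On the literal text it describes only the second fortnight. Mild or moderate stinging that begins at home and settles before Week 2 would not appear in that table, in either arm, and could not be recovered later.

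**Working it through.** The plan gives no figure to reproduce. The check sets the recall rule against the visit calendar.

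**Inputs**
- Visits at Days 0, 14, 28 and 56; Week 2 window +/-3 days, that is Days 11 to 17 (section 1.3).
- Subject ratings at Days 0, 28 and 56 (sections 5.1.8 and 1.3).
- Recall runs from the previous study visit (section 5.1.8).
- Once-daily dosing for 8 weeks: 8 x 7 = 56 applications, approximately.

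**Coverage under the literal rule**

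| Rating | Period covered |
|---|---|
| Baseline | Day 0 application only |
| Week 4 recall | about Day 14 to Day 28 |
| Week 8 recall | about Day 28 to Day 56 |

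**Size of the gap.** If the Week 2 visit falls on Day D and that day's on-site dose counts as inside the Week 4 recall, the uncovered applications run from Day 1 to Day D - 1, which is D - 1 applications.

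- D = 14: 13 applications; 13/56 = 23%.
- D = 11: 10 applications (Days 1-10); 10/56 = 18%.
- D = 17: 16 applications (Days 1-16); 16/56 = 29%.

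The window around Week 4 does not change this, because the Week 8 recall starts wherever the Week 4 visit falls.

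**Can another source fill Days 1-13?**
- *Footnote d* states no look-back, so it neither contradicts nor repairs section 5.1.8.
- *Investigator tolerability rating:* also absent at Week 2, and it grades visible irritation rather than sensation.
- *Adverse events:* assessed at Week 2 (section 5.1.10), with an open question and diary review (section 5.7.4). Section 5.7.1 names as adverse events those application site reactions that need intervention or a pause or stop in dosing. Sensation below that level need not be recorded.
- *DLQI at Week 2:* item 1 asks about itch, soreness, pain and stinging over the preceding week, roughly Days 7-14. It is one combined item and does not separate disease from treatment.
- *Scalpdex at Week 2:* asks whether the scalp hurts over the preceding four weeks. At Week 2 that period includes time before treatment, and it concerns the scalp only.

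None of these asks what the 0-3 scale asks, namely the sensation 10-15 minutes after application.

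**With the recall run from the last tolerability assessment.** The Week 4 recall covers Day 0 to Day 28 and the Week 8 recall Day 28 to Day 56. No application days are left uncovered.

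**The case against.** The strongest reply is that one phrase carries the whole point and may be loose drafting for the last assessment. The first exposure is rated in real time, the scores are only described, and no endpoint, sample size, error rate or eligibility rule uses them. The rule for interrupting treatment in section 5.9 uses the investigator's Dermal Response score, not this scale. Sensation that persists past Week 2 enters the Week 4 recall anyway. All of this stands as to severity. It does not remove the gap: neither section 5.1.8 nor footnote d states the longer look-back, and sites that guess the intent would ask about a different period from sites that follow the text.

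Three stronger readings are tempting, and the documents do not support them.

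- *A reader might infer that the supervised Week 2 dose also goes unrated.* It is given at the Week 2 visit, so a recall that starts at that visit can include it. What can be said is that no rating is scheduled 10-15 minutes after it.
- *A reader might infer that early stinging is invisible, or that nobody asks about the first two weeks.* The Week 2 adverse event query, the diary with its comment section, DLQI item 1 and Scalpdex all ask something relevant. They do not replace the 0-3 scale, but they are not nothing.
- *A reader might infer that application site reactions are adverse events only above the stated threshold.* Section 5.7.1 says that such reactions are adverse events if they meet it; the word 'only' is not there. The restrictive reading is plausible, and on either reading the more serious reactions are recorded.

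**Conclusion.** The gap is real on the plain text and minor in consequence. The subject's 0-3 scale leaves out home applications on about Days 1-13: 13 of about 56 (23%), with a range of 10 to 16 applications (18% to 29%) across the Week 2 window. This assumes that sites follow section 5.1.8 literally, that dosing is once daily for 8 weeks, and that the Week 2 on-site dose falls within the Week 4 recall.

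What is lost is milder, transient sensation early in treatment, in a descriptive tolerability summary. Efficacy endpoints, power and error rates are untouched.

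**What to change.** In section 5.1.8, replace the look-back to the previous visit with *since the last local tolerability assessment*. Add the same look-back to Schedule footnote d, which now states none, so that the two places agree.

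The cost is one phrase in each place. The drawback is that the Week 4 recall lengthens from about two weeks to about four, with the loss of accuracy that longer recall may bring.

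An optional alternative is to add the single-item subject rating at the existing Week 2 visit, with recall since Baseline. That keeps the recall at two weeks and needs no new visit. It is a preference rather than a correction, since section 5.1.8 and the Schedule agree on Baseline, Week 4 and Week 8.

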5.1.9 Pigmentation Assessment

The Investigator will assess for pigmentation in areas affected previously and/or currently by seborrheic dermatitis at the following visits:

Screening, Baseline, Weeks 2, 4, 8 and 9.

Hypopigmentation and hyperpigmentation will be scored individually using a 0-3 scale: '0' for none, '1' for mild, '2' for moderate, and '3' for severe.

5.1.10 Adverse Events

Adverse events (AEs) will be collected beginning at informed consent and assessed at the following visits and throughout the study:

Screening, Baseline, Weeks 2, 4 and 8, and 9

AE collection will end upon completion of study participation for subjects who complete or early terminate from the study without any new or ongoing AEs. Subjects with new or ongoing related AEs upon study completion or early termination will be followed for up to one month after the end of treatment until the symptoms or clinically significant abnormal laboratory test value(s) return to normal or acceptable levels, as judged by the Investigator.

Treatment emergent AEs will be followed in the clinic for up to one month at the Investigator's discretion until resolved or otherwise judged as clinically stable.

For further details on Adverse Events, see Section 5.7.

5.2 Efficacy Evaluations

5.2.1 Investigator Global Assessment (IGA)

Investigator's Global Assessments ('whole body' and 'intertriginous area') will be performed at the study visits listed below. The IGA should be completed prior to any other physician assessments.

Screening, Baseline, Weeks 2, 4, 8, and 9

The IGA is a static evaluation of qualitative overall seborrheic dermatitis severity. This global assessment scale is an ordinal scale with five severity grades (reported only in integers of 0 to 4). Each grade is defined by a distinct and clinically relevant morphologic description that minimizes inter-observer variability.

Every effort must be made for the same Evaluator to complete the IGA for the subject at every study visit, particularly for Baseline and Week 8.

Investigator Global Assessment of Disease (IGA)

Score	Description
0	Completely clear: No erythema, no scaling (hypo-hyperpigmentation can be present)
1	Almost clear: Residual slight erythema and/or trace amounts of scaling
2	Mild: Pink to red color and/or slight scaling
3	Moderate: Distinct redness and/or clearly visible scaling
4	Severe: Severe erythema (intense, fiery red) and/or severe scaling (coarse, thick scales with flaking onto clothes or skin)

5.2.2 Overall Assessment of Erythema

Overall Assessment of Erythema will be performed at the following study visits:

Screening, Baseline, Weeks 2, 4, 8, and 9

Overall Assessment of Erythema is a static qualitative evaluation, involving an ordinal scale with 4 severity grades (reported only in integers of 0 to 3). Each grade is defined by a distinct and clinically relevant morphologic description that minimizes inter-observer variability.

Every effort must be made for the same Evaluator to complete the Overall Assessment of Erythema for the subject at every study visit, particularly for Baseline and Week 8.

Symptom	Score	Description
Erythema	0	None: No evidence of erythema
	1	Mild: Barely perceptible erythema which is faint or patchy
	2	Moderate: Distinct erythema,
	3	Severe: Intense (fiery red) erythema

Overall Assessment of Erythema

5.2.3 Overall Assessment of Scaling

Overall Assessment of Scaling will be performed at the following study visits:

Screening, Baseline, Weeks 2, 4, 8, and 9

Overall Assessment of Scaling are static qualitative evaluations, involving an ordinal scale with 4 severity grades (reported only in integers of 0 to 3). Each grade is defined by a distinct and clinically relevant morphologic description that minimizes inter-observer variability.

Every effort must be made for the same Evaluator to complete the Overall Assessment of Scaling for the subject at every study visit, particularly for Baseline and Week 8.

Overall Assessment of Scaling

Symptom	Score	Description
Scaling	0	None: No scaling evident on lesions
	1	Mild: Barely detectable, scattered, small flaking scales
	2	Moderate: Scales clearly visible and prominent
	3	Severe: Coarse, thick scales, with flaking into clothes or skin

5.2.4 Body Surface Area (BSA)

BSA Assessments will be performed as follows:

Screening, Baseline, and Week 8

The BSA affected by seborrheic dermatitis will be determined by the subject's hand method, where the subject's hand (including fingers) surface area is assumed to equal 1% of body surface area (BSA).

5.2.5 Worst Itch Numerical Rating Scale (WI-NRS)

Given that itch is an important symptom of seborrheic dermatitis, a WI-NRS assessment is included in the present study. A responder analysis will be performed to evaluate achievement of a 4-point reduction of WI-NRS, which has been described as optimal for demonstrating a level of clinically meaningful improvement in itch severity in other skin conditions, including other forms of eczema (Yosipovitch 2019) and psoriasis (Kimball 2016).

WI-NRS Assessments will be performed as follows:

Screening, Baseline, Weeks 2, 4, and 8

The WI-NRS has been developed as a simple, single item to assess the patient-reported severity of this symptom at its highest intensity during the previous 24-hour period. (Naegeli 2015). The WI-NRS will be determined by asking the subject's assessment of worst itch over the past 24 hours. The scale is from '0 to 10' ("no itch" to "worst imaginable itch"). Subjects will complete the WI-NRS pruritus assessment.

No itch

Worst imaginable itch

5.2.6 Scalpdex

The Scalpdex will be completed as follows:

Screening, Baseline, Weeks 2, 4, and 8

Subjects will complete the Scalpdex. See Appendix 5 for the Scalpdex.

5.2.7 Dermatology Life Quality Index (DLQI)

The DLQI will be completed as follows:

Screening, Baseline, Weeks 2, 4, and 8

Subjects will complete the DLQI. See Appendix 4 for the DLQI.

5.2.8 Dermal Imaging

Medical photography will be performed at selected sites at Baseline, Weeks 2, 4, and 8 using Canfield photography equipment. Photography should be focused on single lesions or specific body sections (e.g. arm). Body or half body photos should only be taken if necessary. All efforts will be made to de-identify the subjects. Subjects who are unwilling to participate in the medical photography will be allowed to opt out of this procedure and documented on the informed consent. Refer to the current Photography Manual for instructions regarding photography.

